For PCMS to maximally enhance motor output and dexterity, it must reliably activate as many corticospinal-motoneuronal synapses as possible. However, corticospinal tract recruitment via TMS varies significantly with the brain state at the exact moment of TMS delivery (Sauseng et al. 2009; Berger et al. 2014; Zrenner et al. 2018; [name] et al. 2019a, [name] et al. 2019b; Bergmann et al. 2019). Yet, current approaches deliver PCMS irrespective of the brain state. Delivering PCMS in this way ensures that only a fraction of stimuli occur during brain states that are likely to maximally recruit alpha motoneurons. By delivering PCMS during brain states reflecting strong alpha motoneuron recruitment, STDP_{LTP} could be induced at a greater proportion of corticospinal-motoneuronal synapses, leading to greater PCMS-induced gains in corticospinal transmission and hand function. We recently developed a novel machine learning framework that successfully identifies brain states during which TMS strongly or weakly activates the corticospinal tract. Results of this work show that individually-defined brain states predict TMS-related activation of the corticospinal tract ([name] and Quentin 2021), suggesting that delivering PCMS during these states could improve PCMS's efficacy.

The long-term goal of this work is to improve voluntary hand muscle activation and manual dexterity in chronic stroke patients with residual corticospinal connections. As first steps towards this goal, the efficacy of brain state-dependent PCMS must be established in the healthy nervous system. The purpose of this project is to establish this efficacy in healthy adults. The aims of this study are to:

1) validate the accuracy of real-time brain state-dependent TMS

2) determine if TMS activates more alpha motoneurons when applied during brain states reflecting strong corticospinal recruitment than during brain states reflecting weak corticospinal recruitment or random brain states.

3) determine if delivering PCMS during brain states reflecting strong corticospinal recruitment enhances the behavioral and neurophysiological effects of PCMS.

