Real-time EEG analysis: The EEG system will stream data in real-time to a dedicated computer. This computer will analyze the data in real time to identify brain states associated with strong or weak corticospinal tract recruitment (see above), or a random mixture of the two. When desired states are identified, either a single TMS pulse (see *Evaluation of state-targeting* accuracy) or the TST (see *TST assessment*) will be triggered. *Evaluation of state-targeting accuracy:* <= 150 single TMS pulses will be applied to the scalp at <= 120% of scalp RMT during EEG recordings.

Calculation of ISIs for TST assessment: The following stimulation procedures will be performed to calculate the ISIs for TST assessment.

- 1. <= 25 Single-pulse TMS to the scalp at <= 120% of scalp RMT
- 2. <= 25 Single-pulse PNS to the left wrist at <= 120% of M-max
- 3. <= 25 Single-pulse PNS to the left Erb's point at <= 120% of M-max

TST assessment: The TST will be applied according to an established protocol (Magistris et al. 1998) using consecutive application of TMS (<= 120% of scalp RMT), PNS at the left wrist (<= 120% of M-max), and PNS at the left Erb's point (<= 120% of M-max). The delays between each stimulus will be individualized based on each participants central and peripheral conduction times (see *Calculation of ISIs for TST assessment*). The TMS portion of the TST will be timed to occur during brain states reflecting strong corticospinal tract recruitment, weak corticospinal tract recruitment, or random brain states, using real-time EEG analysis. <= 50 TST applications will be performed per brain state condition.

Experiment 3

Design: within-subjects, single group Population: healthy adults (≥ 18 years old)

Conditions: At least 24 hours will elapse between sessions.

- 1. Active PCMS delivered during brain states reflecting strong corticospinal recruitment
- 2. Active PCMS delivered during brain states reflecting weak corticospinal recruitment
- 3. Active PCMS delivered during random brain states

- 4. Control PCMS delivered during brain states reflecting strong corticospinal recruitment
 - a. The order of conditions will be counterbalanced
 - b. Participants may complete one, two, three or four of the conditions

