Spinal excitability measurements: <= 25 single PNS pulses to the left wrist at <= 120% of M-max. Measurements will be taken immediately before PCMS and at 0, 20 and 40 minutes after PCMS.

Voluntary motor output measurements: <= 5 maximum voluntary contractions of the FDI, each lasting <= 5 seconds. Measurements will be taken immediately before PCMS and at 0, 20 and 40 minutes after PCMS. Manual dexterity measurements. <= 5 attempts of the 9-hole peg test. Measurements will be taken immediately before PCMS and at 0, 20 and 40 minutes after PCMS.

5 Data Analysis

Describe the data analysis plan, including any statistical procedures or power analysis. To input text, click in the light grey area below.

Experiment 1:

- 1. Primary outcome: Amplitude of MEPs evoked during brain states reflecting strong, weak, and/or random corticospinal tract recruitment
 - a. This outcome will be evaluated using linear-mixed effects models (fixed effect of state, random effect of subject) with alpha equal to 0.05.

Experiment 2:

- 1. Primary outcome: amplitude of FDI muscle response after TST application during brain states reflecting strong, weak, and random corticospinal tract recruitment.
- 2. Secondary outcome: area under the curve of FDI muscle response after TST application during brain states reflecting strong, weak, and random corticospinal tract recruitment.
 - a. Both outcomes will be evaluated using linear mixed-effects models (fixed effect of state, random intercept of subject) with alpha equal to 0.05.

Experiment 3:

- 1. Primary outcomes: Maximum FDI force output, FDI activation (calculated using the root-mean-square of EMG signals obtained during FDI contractions)
- 2. Secondary outcome: Number of pegs placed per attempt at the 9-hole Pegboard test.
- 3. Exploratory outcomes: Amplitudes of MEPs produced by scalp TMS, amplitudes and persistence of Fwaves evoked by wrist PNS
 - All outcomes will be evaluated before and after PCMS. Outcomes will be analyzed using linearmixed effects models (fixed effects of condition and time point, random intercept of subject).
 Main effects will be evaluated using likelihood ratio tests, and p-values from post-hoc contrasts will be corrected for multiple comparisons. Alpha will be equal to 0.05.

STUDY ELEMENT IDENTIFICATION

6 Study Elements

Click on the check box (or double click and type an "X" if using Google Docs) each procedure included in your study.

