- The real-time EEG algorithm will be used to deliver <= 150 single TMS pulses during brain states associated with strong corticospinal recruitment, <= 150 single TMS pulses during brain states associated with weak corticospinal recruitment, and/or <=150 single TMS pulses during randomly selected brain states, for a total of <= 450 single TMS pulses. During this time, participants will rest quietly with their eyes open (Zrenner et al. 2018; [name] et al. 2020).

- We may also record EEG signals at any time point during testing while participants rest quietly with their eyes open.
- The EEG cap and EMG electrodes will be removed and participants will leave the laboratory.
- If participants are asked to complete two sessions, the same experimental procedures described above may be used during the second session. The second session may be used to evaluate between-day reliability of the measurements made during the first session. At least 24 hours will elapse between sessions.

Experiment 2:

- The participant and research team member will review and discuss the informed consent document.
- Eligibility will be formally determined by the research team member by reviewing a list of the inclusion and exclusion criteria with the participant (see attachments).
- Participants will complete a short demographics survey.
- The EEG cap containing will be positioned on the participants head according to the 10-20 International EEG system (Seeck et al. 2017). The scalp beneath each electrode may be cleaned with alcohol, and an electrolytic gel will be applied beneath each electrode. Afterwards, the scalp may be lightly abraded using a blunt needle.
- The skin on the left hand, left wrist, and left Erb's point will be cleaned using isopropyl alcohol. EMG electrodes will be attached to a maximum of 5 hand and wrist muscles using medical grade adhesive. PNS electrodes will be attached to the left wrist and left Erb's point using medical grade adhesive. A ground electrode will attached to the dorsum of the hand in the same manner.
- The scalp TMS hotspot will be determined as the site of the scalp producing the most reliable focal muscle twitch within the left FDI. The scalp RMT will be determined using an automatic threshold tracking tool (Awiszus and Borckhardt 2011) as the minimum stimulation intensity needed to elicit an MEP of 50 microvolts in peak-to-peak amplitude in response to 50% of stimuli. EMG and EEG signals may be recorded for offline quality control analysis.

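### Experiments 1 and 2 do not state the unit of analysis or include a by-subject state effect; if single responses are modelled, the test of state may use too small an error term

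*Combined protocol and SAP*

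**What the plan says.** Section 5 (Data Analysis) gives one line of model for each experiment.

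- **Experiment 2**, TST response amplitude (primary) and area under the curve (secondary): "Both outcomes will be evaluated using linear mixed-effects models (fixed effect of state, random intercept of subject) with alpha equal to 0.05".
- **Experiment 1**, primary outcome: "Amplitude of MEPs evoked during brain states reflecting strong, weak, and/or random corticospinal tract recruitment". The model is "linear-mixed effects models (fixed effect of state, random effect of subject) with alpha equal to 0.05". Whether the random effect is an intercept, a slope or both is not said.

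Each person gives many responses per state. For Experiment 2, section 4 (Design and Methodology) says: "<= 50 TST applications will be performed per brain state condition". For Experiment 1, section 11 (Procedure Description) allows at most 150 pulses in each of three states, "for a total of <= 450 single TMS pulses". Section 14 sets a target of 20 people per experiment.

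Nowhere do the documents say whether a row of the analysis data is one response or one mean per participant and state. They name no subject-by-state term, degrees-of-freedom method or robust variance for these models. Section 3 (Study Background) describes the states as specific to each person: "individually-defined brain states predict TMS-related activation of the corticospinal tract".

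**The concern.** A model with a fixed state effect and only a subject intercept assumes that the strong-minus-weak difference is the same in everyone. Fitted to single responses, it treats all of a person's pulses in a state as independent replicates of that common difference. At the maxima that is 20 × 3 × 50 = 3,000 rows in Experiment 2 and 20 × 3 × 150 = 9,000 in Experiment 1. The hypotheses concern healthy adults, of whom there are 20.

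There are two reasons to expect the difference to vary between people. States are learned separately for each participant, so decoding quality is likely to differ. Also, condition order is randomized, but the documents do not say whether conditions are delivered in blocks or interleaved. With blocks, slow drift in excitability creates subject-by-state variance even if state has no effect in anyone. An intercept absorbs neither source.

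At stake are the p-value and interval for the primary outcome of each experiment.

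**Working it through.** **Inputs from the documents.** N = 20 people (section 14); K = 3 states; n = up to 50 responses per state in Experiment 2 (section 4) and up to 150 in Experiment 1 (section 11); alpha 0.05 (section 5), taken as two-sided.

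**Assumed input.** σ is the SD of single responses within a person and state. τ is the SD of a person's departure from the average effect of a state. The documents give neither, so τ/σ is varied from 0 to 0.20. The average state effect is set to zero.

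**The plan's own figures.** N = 20 cannot be reproduced, because section 15 argues from the sample sizes of earlier studies and gives no effect size, SD or power. The nominal alpha can: at τ = 0 the intercept-only model on single responses gives 5%.

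**Step 1: variance of a pairwise state contrast.**

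- Intercept-only model on single responses: 2σ²/(nN)
- True: 2σ²/(nN) + 2τ²/N
- Ratio: f = 1 + nτ²/σ²

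N cancels, so recruiting more people does not reduce the problem, and more pulses per person enlarge it.

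**Step 2: error rates (large-sample).** With three states the omnibus statistic has 2 numerator degrees of freedom, so the actual type I error is 0.05^(1/f). Coverage of a nominal 95% pairwise interval is 2Φ(1.96/√f) − 1. Worked example, Experiment 2 at τ/σ = 0.20: f = 1 + 50 × 0.04 = 3; the true SE is √3 = 1.73 times the model SE; type I error 0.05^(1/3) = 36.8%; coverage 2Φ(1.13) − 1 = 74.2%.

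**Step 3: simulation.** 40,000 balanced trials per setting, testing state against the pooled residual, as an intercept-only model does.

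| Experiment | τ/σ | f | Omnibus type I, formula | Omnibus type I, simulated | Coverage, formula | Coverage, simulated |
|---|---|---|---|---|---|---|
| 2 (n = 50) | 0.05 | 1.125 | 7.0% | 7% | 93.5% | 94% |
| 2 | 0.10 | 1.5 | 13.6% | 13% | 89.0% | 90% |
| 2 | 0.15 | 2.125 | 24.4% | 24% | 82.1% | 83% |
| 2 | 0.20 | 3 | 36.8% | 36% | 74.2% | 75% |
| 1 (n = 150), if intercept only | 0.05 | 1.375 | 11.3% | 11% | 90.5% | 91% |
| 1 | 0.10 | 2.5 | 30.2% | 30% | 78.5% | 79% |
| 1 | 0.15 | 4.375 | 50.4% | 50% | 65.1% | 66% |
| 1 | 0.20 | 7 | 65.2% | 64% | 54.1% | 55% |

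Pairwise type I error is 100% minus coverage: at τ/σ = 0.20, about 25% in Experiment 2 and 45% in Experiment 1. The random condition is optional in Experiment 1. With two states only and n = 150, simulated type I error is 9%, 22%, 35% and 46% across the same τ/σ range.

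**Step 4: fewer pulses.** At half the maxima and τ/σ = 0.10, f = 1.25 (n = 25) and 1.75 (n = 75). Type I error is 0.05^(1/1.25) = 9% and 0.05^(1/1.75) = 18%.

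**Step 5: fitted mixed models.** 300 random-intercept fits (two states, n = 50, SD of the state difference between people 0.2σ, so τ = 0.2σ/√2 and f = 2) rejected in 17.7%. The formula gives 2(1 − Φ(1.96/√2)) = 16.6%. With no such variance, 5.0% rejected.

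**Step 6: the alternative.** Testing state on participant-by-state means, with (20 − 1)(3 − 1) = 38 error degrees of freedom, gave about 5% in every setting. This assumed equal subject-by-state variance across states. A random-slope model was not fitted. All checks ignore skewed MEP amplitudes and serial correlation between pulses.

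**The case against.** The strongest reply is that section 5 is silent on the unit of analysis rather than wrong about it. An amplitude by state can be a participant's mean as well as a single response, and on means a subject intercept is adequate. This stands: that the plan fits pulse-level data is something a reader might infer, and the outcome wording favours it, but the documents do not say so.

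A reader might also take both experiments to be intercept-only. That is written for Experiment 2. Experiment 1's wording could include a slope, so its larger figures are conditional on an intercept being meant.

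A third reply is that if state matters for nobody and there is no drift, τ is zero and the test is valid even on single responses. This also stands. Individually decoded states make variation likely, not certain, and no value is given. At τ/σ = 0.05 the effect in Experiment 2 is small.

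Two further inferences are tempting and unsupported. One is that participants with two sessions count double: section 11 says the second session may serve to assess between-day reliability, and nothing says its data enter the primary model. The other is that Experiment 3 rests on these tests: no passage makes it conditional on their results, and it repeats brain-state discovery itself.

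What the reply does not remove is that a prespecified primary analysis permits one reading that is valid and another, the more natural one, that may not be.

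**Conclusion.** The concern holds in conditional form. The plan leaves the unit of analysis open in both experiments and the random-effects structure open in Experiment 1, and it writes an intercept-only structure for Experiment 2. If single responses are modelled with that structure and the state effect or block drift varies between people, the intervals are too narrow and type I error exceeds 5%.

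Over the assumed range the excess runs from slight (7% in Experiment 2 at τ/σ = 0.05) to severe (36% in Experiment 2, and 64% in Experiment 1 if intercept-only, at 0.20). These are omnibus figures at the maximum pulse counts; pairwise inflation is smaller, and so is inflation with fewer pulses. The documents do not support saying that the planned p-values are certainly wrong.

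**What to change.** In section 5, for Experiments 1 and 2, state the unit of analysis and choose one of two models:

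1. Analyse one mean per participant and state, with a fixed effect of state and a random intercept for subject.
2. Analyse single responses, with a fixed effect of state and a by-subject random effect of state (random slopes or a subject-by-state term) as well as the subject intercept, and test with Satterthwaite or Kenward-Roger degrees of freedom.

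The first is simpler and avoids convergence problems with 20 people. Session terms are needed only if second-session data enter the primary model, and the plan should say whether they do.

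The cost is a sentence of analysis text and wider intervals wherever the state effect varies between people. No additional data or participants are required.

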FORM: IRB Proposal - Standard Submission

NUMBER HRP-UT901 VERSION DATE 8/29/2024

GENERAL STUDY INFORMATION

Use for greater than minimal risk studies and minimal risk studies that fit into one or more expedited categories (see Section 5.3 of our Policies & Procedures for details regarding expedited research).

Do NOT submit this form if the study will qualify for exempt review, instead submit HRP-UT902 IRB Proposal – Exempt Submission Form found in the document Library.

If you are only using secondary data that will not be initially collected solely for this research project, use HRP-UT903 Template IRB Proposal Secondary Use form instead.

For studies following a multi-center or sponsor protocol, please use this guidance to assist in your completion of this form.

For questions regarding definitions, policies, or terms referenced below see the policies and procedures manual.

Please note, Word online does not support Word checkboxes. Please download the file and use your desktop version of Microsoft Word.

1 Review Type (Choose one)

Click on the check box (or double click and type an "X" if using Google Docs) the one review type that applies.

Please note: Expedited Review does not refer to the timeliness of the review of your protocol, but specific categories of research defined by ORHP. If you would like help determining which type of review is most appropriate for your study please contact the Office of Research Support and Compliance: https://research.utexas.edu/ors/about-ors/contact-us/.

a 🖂 Full Board Review – Greater than Minimal Risk Research

b Expedited Review – Minimal Risk Research

2 Research Hypothesis

To input text, click in the light grey area below.

Hypothesis 1 (Experiment 1): Transcranial magnetic stimulation (TMS) can be accurately applied during brain states reflecting strong and weak corticospinal tract recruitment.

Hypothesis 2 (Experiment 2): Transcranial magnetic stimulation (TMS) applied during brain states reflecting strong corticospinal tract recruitment will activate more alpha motoneurons than identical TMS applied during brain states reflecting weak corticospinal tract recruitment or random brain states.

Hypothesis 3 (Experiment 3): Delivering paired corticospinal-motoneuronal stimulation (PCMS) during brain states reflecting strong corticospinal tract recruitment will increase (a) corticospinal transmission, (b) voluntary

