hand muscle activation, (c) voluntary hand muscle force production, and (d) hand dexterity more than identical PCMS applied during brain states reflecting weak corticospinal tract recruitment or random brain states.

3 Study Background

To input text, click in the light grey area below.

Stroke is the leading cause of long-term disability in the United States (Go et al. 2013) and commonly disrupts the corticospinal tract (Twitchell 1951). The presence of residual corticospinal connections is one of the best prognostic markers of post-stroke motor function and recovery potential (Stinear et al. 2007), indicating that the most serious and long-lasting stroke-related motor deficits are caused by corticospinal tract disruption. Interventions capable of strengthening residual corticospinal connections are thus promising candidates for improving motor function after stroke. Paired cortico-motoneuronal stimulation (PCMS) can strengthen corticospinal connections in healthy adults (Taylor and Martin 2009; Bunday and Perez 2012) and patients with corticospinal tract disruption caused by spinal cord injury (Bunday and Perez 2012). PCMS involves repeatedly delivering precisely-timed pairs of non-invasive peripheral stimuli (via transcutaneous peripheral nerve stimulation) and cortical stimuli (via transcranial magnetic stimulation) such that they induce long-term potentiation via spike-timing dependent plasticity (STDP_{LTP}) at corticospinal-motoneuronal synapses, which are essential to human dexterity (Lemon 2008).

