 - Active PCMS during brain states reflecting weak corticospinal recruitment, with the delay between scalp TMS and wrist PNS equal to the Active PCMS delay.
 - Active PCMS during random brain states, with the delay between scalp TMS and wrist PNS equal to the Active PCMS delay.
 - Control PCMS during brain states reflecting strong corticospinal recruitment, with the delay between scalp TMS and wrist PNS equal to the Control PCMS delay.
- Participants will complete post-PCMS measurements of corticospinal excitability, spinal excitability, voluntary motor output, and manual dexterity (see Design and Methodology) immediately, 20 minutes, and 40 minutes after PCMS is complete. EMG signals will be recorded during all measurements and processed offline to obtain outcome measures. EEG may recorded for offline quality control analysis.
- EEG, EMG and PNS electrodes will be removed and participants will leave the laboratory.

SUBJECT POPULATION

12 Protected Subject Populations

Click on the check box (or double click and type an "X" if using Google Docs) each population, if they are specifically studied for this research.

13* Research Participant Information

Describe the research population.

*For multiple research populations (e.g., teachers, students, and parents), copy this section as necessary to describe your population.

a Participant Group Name

To input text, click in the light grey area below. Healthy adults

b Minimum Age

To input text, click in the light grey area below. 18

c Maximum Age

To input text, click in the light grey area below. none

d Inclusion Criteria

To input text, click in the light grey area below. Right-hand dominance Willingness to participate

Ability to provide informed consent

e Exclusion Criteria

To input text, click in the light grey area below.

History of major neurological, orthopedic, psychiatric, or cardiovascular disease Presence of contraindications to TMS or PNS (Keel et al. 2000), including:

- 1) history of adverse reactions to TMS or PNS
- 2) history of stroke or head injury
- 3) metal in head, eyes, neck, chest/trunk, or arms, including but not limited to shrapnel, surgical clips, fragments from metalworking, fragments from welding
- 4) implanted devices
- 5) history of frequent and severe headaches or migraines
- 6) immediate family history of seizure or epilepsy
- 7) personal history of seizure or epilepsy
- 8) current, suspected, or planned pregnancy

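### Does Experiment 3 need a written rule for its two primary outcomes and for the family of post-hoc contrasts before its multiplicity control can be trusted?

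*Combined protocol and SAP*

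**What the plan says.** Section 5 (Data Analysis), Experiment 3, lists two primary outcomes: "Primary outcomes: Maximum FDI force output, FDI activation (calculated using the root-mean-square of EMG signals obtained during FDI contractions"). The 9-hole peg test is secondary; MEPs and F-waves are exploratory. All are analysed by linear mixed-effects models with "fixed effects of condition and time point, random intercept of subject". For inference, "Main effects will be evaluated using likelihood ratio tests", and "p-values from post-hoc contrasts will be corrected for multiple comparisons". Alpha is 0.05.

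Section 4 sets four conditions: active PCMS in strong, weak and random states, and control PCMS in the strong state. For voluntary motor output it says: "Measurements will be taken immediately before PCMS and at 0, 20 and 40 minutes after PCMS". Section 11 repeats the post-PCMS times as "immediately, 20 minutes, and 40 minutes after PCMS is complete".

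Hypothesis 3 in section 2 is directional. It says that PCMS "during brain states reflecting strong corticospinal tract recruitment will increase (a) corticospinal transmission", and it goes on to voluntary "hand muscle activation, (c) voluntary hand muscle force production, and (d) hand dexterity more than identical PCMS applied during brain states reflecting weak" or random states. Activation is item (b) and force is item (c).

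Section 5 does not say whether force and activation are separate conclusions, alternatives or jointly required. It does not list the contrasts, name the correction, define its family or single out a post-PCMS time.

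**The concern.** A likelihood ratio test of condition across four conditions, one of them a control, cannot show that the strong state beats the weak or random state. Nor can a test of time. The claim in Hypothesis 3 therefore rests on the post-hoc contrasts, and these are the part left undefined.

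Four conditions give six pairs. Three post-PCMS times and two outcomes multiply the possible families. If the family is chosen once the p-values are known, the same result can be called positive or negative. Under Holm or Bonferroni, a smallest p-value of 0.01 passes in a family of two and fails in a family of six. With two primary outcomes and no combining rule, success on either might also be claimed at 0.05 each, which would raise the overall error above 5%.

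**Working it through.** **Inputs.** Alpha 0.05, two primary outcomes and the model terms (section 5); four conditions and three post-PCMS times (section 4); two hypothesised contrasts, strong vs weak and strong vs random (section 2); target N = 20, raised from 14 (sections 14 and 15). No effect size, SD, power or corrected threshold is given, so N = 20 cannot be reproduced. A two-sided alpha is assumed.

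**1. Thresholds.** Bonferroni, or the first Holm step, is 0.05/m.

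| Family | m | 0.05/m | Available from the model as written? |
|---|---|---|---|
| Two hypothesised contrasts, one outcome | 2 | 0.025 | yes |
| Two contrasts × two outcomes | 4 | 0.0125 | yes |
| Six pairs, one outcome | 6 | 0.0083 | yes |
| Six pairs × two outcomes | 12 | 0.0042 | yes |
| Six pairs × three times | 18 | 0.0028 | no |
| Six pairs × three times × two outcomes | 36 | 0.0014 | no |

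The last two rows need condition contrasts that differ by time. With condition and time point as additive terms, a condition contrast is the same at every time. The range from the model as written is therefore 0.025 to 0.0042, a ratio of 6. It reaches 0.0014 (a ratio of 18) only if a condition-by-time term is added.

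**2. Does a p-value of 0.01 change sides?** Under Holm or Bonferroni, 0.01 < 0.025 passes and 0.01 > 0.0083 fails. Under Tukey over the six pairs of four conditions, a raw p of 0.01 becomes 0.045 with 19 degrees of freedom, 0.048 with 57 and 0.049 in the large-sample limit. It passes. The reversal thus depends on the method and not on family size alone.

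**3. False-positive rate per outcome.** The event is strong > weak or strong > random declared at any post-PCMS time when nothing differs. Assumptions: 20 complete participants, paired t-tests on change from pre-PCMS, Holm, correlation 0.5 between times, 120,000 simulated trials. Only favourable results count, so one two-sided 0.05 test would give 2.5%.

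- Two contrasts, corrected separately at each time: 6.1% (4.8% if the time correlation is 0.8)
- Six pairs, corrected separately at each time: 2.3%
- 18 contrasts per outcome: 0.8%
- 36 contrasts across both outcomes: 0.4%
- Two contrasts on the mean of the three times: 2.3%

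Only the first reading exceeds 5%, because it leaves three times uncorrected. If control PCMS is lower by an assumed d = 1 and brain state has no effect, the first four readings give 6.1%, 4.1%, 1.3% and 0.6%. The 18-contrast family under false-discovery-rate control gives 6.6%.

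**4. Two outcomes.** If success on either of two independent 0.05 tests counted, the error would be 1 − 0.95 × 0.95 = 0.0975. It falls to 0.065 at correlation 0.95. For the contrasts in step 3 (two per time), either-outcome success gives 11.8% at outcome correlation 0 and 7.9% at 0.95. If both outcomes are required, the range is 0.4% to 4.2%. If each outcome supports its own conclusion, the rates in step 3 apply.

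**The case for a change.** The strongest reply is that a promise of correction without a family does not fix a decision rule, and that section 5 is where the rule belongs. Four points follow.

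- *The hypothesis cannot be tested by the additive model, so the time family must enter.* An additive condition contrast averages values before and after PCMS, so it does not isolate change. Testing Hypothesis 3 does call for a change score or a condition-by-time term. This stands, but it concerns the model terms, not the correction. It also does not force a contrast at each time: the mean of the three times gives one contrast per comparison and a rate of 2.3%.
- *The method matters as well as the family.* True: 1.3% under Holm against 6.6% under false-discovery-rate control for the same 18 contrasts. The second figure needs an assumed control deficit of d = 1.
- *Power depends on the choice.* With 20 complete pairs, the paired difference detectable at 80% power is d = 0.66 uncorrected, 0.74 at 0.025, 0.86 at 0.0083 and 1.05 at 0.0014. Complete pairs are not assured, since section 4 lets participants complete one to four conditions. This favours a short family, which the two comparisons in Hypothesis 3 already supply.
- *Either outcome could be claimed.* Nothing in the documents states that rule, and the 11.8% further requires uncorrelated outcomes, although both come from maximal contractions of the same muscle.

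What remains is that the choice is not written down. Even a prescriptive sentence would have to settle whether one or both of strong vs weak and strong vs random must succeed. If both must, each can be tested at 0.05 without Holm; under the two-per-time Holm reading, requiring both at the same time lowers 6.1% to about 0.9%.

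**Conclusion.** The omission is real, but it does not call for a change. No stated figure or rule is wrong: the plan ranks its outcomes, sets alpha at 0.05 and commits to correcting the contrasts. Hypothesis 3 supplies the two comparisons of interest and letters force and activation separately, so an analyst would naturally treat them as two conclusions with a short family each. Several ways of completing the rule are sound, and the documents give no ground for calling one of them right and the rest wrong.

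The size is modest. Thresholds available from the written model run from 0.025 to 0.0042 under Bonferroni or the first Holm step. With no true effect, the per-outcome false-claim rates under Holm are 0.4% to 2.3%, except for 6.1% when two contrasts are corrected separately at each time. That exception is more than twice the 2.5% benchmark, and it drops to 4.8% at a time correlation of 0.8. The rates rest on 20 complete participants, paired t-tests in place of the planned mixed model, and assumed correlations; incomplete conditions would alter them. For a healthy-volunteer study that section 3 presents as a first step, this is a gap that analysts fill sensibly, provided that the report states the contrasts, the method and the family used.
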